6.1.1. Dose Optimization Cohorts

Two pre-defined, escalating dose combinations will be tested in subjects with hematologic malignancies in Part A. Additional cohorts may be added in order to explore alternative dose combinations (Section 3.3). The decision to add additional cohorts will be made upon recommendation of the SET and in agreement with the study sponsor.

Dose escalation above 560 mg for ibrutinib is not permitted. Administration of each study drug in Part A is described in Table 4.

Table 4: Ibrutinib and Nivolumab Dose Levels: Part A (Dose Optimization Cohorts)

| Dosing Cohort ^a | Ibrutinib (daily oral administration) ^b | Nivolumab (IV infusion Day 1 every cycle) ^b |
|----------------------------|---|---|
| A1 | 420 mg | 3 mg/kg |
| A2 | 560 mg ^c | 3 mg/kg |

^a Additional dosing schedules may be explored if recommended by SET and agreed upon by sponsor.

^b On days that both drugs will be administered, the sequence of administration will be nivolumab IV followed by oral ibrutinib

^c The maximum dose of ibrutinib will not exceed 560 mg. The dose of nivolumab will be 3 mg/kg.

6.1.2. Dosing Schedule

Study drugs will be administered as described below in Table 5.

Table 5: Ibrutinib and Nivolumab Dosing Schedule

| | Ibrutinib Run-in, Day -7 to Day 1 | Cycle 1 Day 1 | Cycle 2 Day 1 | Day 1 of every cycle, Cycle 3 and all subsequent cycles |
|---------------------------------|--------------------------------------|---------------------------------|---------------|--|
| | | DLT Determinative Period | | |
| Part A, Cohort A1 and A2 | | | | |
| Ibrutinib | | <-----continuous dosing-----> | | |
| Nivolumab ^a | | 3 mg/kg | 3 mg/kg | 3 mg/kg |
| Part B, Cohort B1 and B2 | | | | |
| Ibrutinib | | <-----continuous dosing-----> | | |
| Nivolumab ^a | | 3 mg/kg | 3 mg/kg | 3 mg/kg |
| Part B, Cohort B3 and B4 | | | | |
| Ibrutinib | | <-----continuous dosing-----> | | |
| Nivolumab ^a | | 3 mg/kg | 3 mg/kg | 3 mg/kg |

^a Nivolumab administered first followed by ibrutinib.

Ibrutinib Run-in Period: In Cohort B1 and B2, to assess pharmacokinetic and pharmacodynamic characteristics of ibrutinib monotherapy, ibrutinib will be given at the recommended Phase 2 dose over an initial period of seven days prior to the first dose of nivolumab (Day -7 to -1).

Nivolumab will be administered on Day 1 of each 14-day treatment cycle.

DLT Period: DLT will be documented over the first 2 cycles beginning with the first concomitant administration of ibrutinib and nivolumab on Day 1 of Cycle 1.

6.2. Ibrutinib Administration

Ibrutinib capsules will be self-administered once daily. Ibrutinib should be taken around the same time each day with approximately 240 mL of water (ie, 8 ounces). The capsules should be swallowed whole and should not be opened, broken, or chewed.

Ibrutinib dosing is outlined in Table 6. On the study days scheduled for serial pharmacokinetic sampling of ibrutinib, the investigator or designee will supervise administration of ibrutinib and the exact time of administration will be recorded in the eCRF or in the laboratory requisition form. On other days, ibrutinib will be self-administered, and a subject diary card will be used to record administration and aid compliance with ibrutinib administration compliance.

Table 6: Ibrutinib Dosing

| Ibrutinib (prescribed dose) | Number of Capsules (of 140mg) |
|-----------------------------|-------------------------------|
| 280 mg | 2 x 1 |
| 420 mg | 3 x 1 |
| 560 mg | 4 x 1 |

If a dose of study drug is missed, it can be taken as soon as possible on the same day with a return to the normal schedule the following day. The subject should not take extra capsules to make up the missed dose. The missed dose will be recorded on the eCRF and must be returned to the site at the next scheduled visit.

Subjects should avoid consuming food and beverages containing grapefruit or Seville oranges for the duration of the study due to cytochrome (CYP) 3A inhibition.

Sufficient study drug required for treatment until the next visit will be dispensed. Unused ibrutinib dispensed during previous visits must be returned and drug accountability records will be updated. Returned capsules must be discarded and may not be re-used in this study or outside the study. Study-site personnel will instruct subjects on how to store study drug for at-home use as indicated for this protocol. Storage instructions are provided in the Site Investigational Product Procedures Manual (SIPPM).

There is limited data on the effects of ibrutinib overdose. No Maximum Tolerated Dose was reached in the Phase 1 study in which patients received up to 12.5 mg/kg/day (1,400 mg). There is no specific antidote for ibrutinib. Subjects who ingest more than the recommended dosage should be closely monitored and given appropriate supportive treatment.

6.3. Nivolumab Administration

Eligible subjects will receive treatment with nivolumab at a dose of 3 mg/kg given as a 60-minute IV infusion on Day 1 of every 14-day cycle. If the subject's weight on the day of dosing differs by > 10% from the weight used to calculate the dose, the dose must be recalculated. All doses should be rounded to the nearest milligram.

There are no premedications recommended for nivolumab on the first cycle. If an acute infusion reaction is noted, subjects should be managed according to guidelines provided in Section 8.11.

Subjects may receive nivolumab infusions with no less than 12 days between doses and no more than 3 days after the scheduled dosing date. A dose given after the 3-day window is considered a dose delay. A maximum delay of 42 days between doses is allowed.

6.3.1. Interactive Web Response System

Drug supply for nivolumab will be managed through IWRS at least for Part B.

For IWRS, the requestor must use his or her own user identification and personal identification number when contacting the IWRS, and will then give the relevant subject details to uniquely identify the subject. Details on the use of IWRS will be provided in the IWRS manual.

The subject should receive their dose of study medication within 1 day of vial assignment following call to IWRS.

6.4. Dose Modifications

Treatment modifications may be made to both ibrutinib and nivolumab. Changes in dose apply only to ibrutinib. Nivolumab will be given at fixed dose, treatment modifications are primarily dose delays.

Adjustments of study drug dose should be overseen by the principal- or sub-investigator(s) unless an immediate safety risk is apparent. The dose adjustments are applicable to all subsequent treatment cycles.

Note: The recommendation to discontinue study therapy applies to both study drugs. If appropriate and after consultation with the Sponsor, subjects may receive ibrutinib alone. Following implementation of amendment 7, treatment with single agent ibrutinib will be discontinued and an End of Trial visit will be performed for patients not scheduled to rollover into long-term extension study CAN3001. Patients scheduled to roll over into Study CAN3001 will continue treatment.

6.4.1. Ibrutinib Dose Modifications

Dose reduction levels for ibrutinib, if required in Section 6.4.3, are listed in Table 7.

Table 7: Dose Reduction for Ibrutinib

| Ibrutinib Dose | 420 mg | 560 mg |
|----------------|--------|--------|
| Dose Level -1 | 280 mg | 420 mg |
| Dose Level -2 | NA | 280 mg |

Ibrutinib dose reductions below 280 mg per day are not permitted and may require discontinuation of study therapy after consultation with the Sponsor. Dose escalations of ibrutinib to the previous higher dose may be considered after consultation with the Sponsor.

In Part A, intra-patient dose escalation may be requested by the investigator and discussed with the medical monitor once a subsequent higher combination dose has been declared acceptable by the SET for subjects who (1) have received at least 4 cycles of combination treatment at the assigned dose level, and (2) have not experienced a DLT or therapy-related SAE. Subjects whose dose has been escalated will not be considered for the safety evaluation in the subsequent dose level and the determination of the RP2D.

6.4.2. Nivolumab Dose Modifications

There will be no dose escalations or reductions of nivolumab allowed. Dose delay is the primary method for managing nivolumab-related toxicities.

6.4.3. Guidelines for Dose Modification

Guidelines for dose modifications following occurrence of general toxicities are listed in Table 8. For immune-related adverse events and other events of clinical interest, guidelines for dose modification are listed in Table 9.

Of note: **Guidelines for the management of immune-related adverse events and adverse events of clinical interest** are provided in Section 8.

If the criterion to resume treatment is met, the subject should restart treatment at the next scheduled timepoint per protocol.

If treatment is delayed > 6 weeks, the subject must be permanently discontinued from study therapy, except as specified in the protocol.

Table 8: Dose Adjustments for Related Non-hematologic and Related Hematologic Toxicities

| Adverse Event | CTCAE Grade | Ibrutinib and Nivolumab * |
|---|---|---|
| *For immune-related toxicities please see Table 9. Additional information may also be found in the latest IB sections (appendix on nivolumab adverse event management, algorithm management sections) Recommendations for the management of immune-related adverse events and adverse events of clinical interest are provided in Section 8. | | |
| Non-Hematologic Toxicity [see separate table for Immune-related toxicities and adverse events of clinical interest) | | |
| General | Grade 1 | Continue therapy. |
| | Grade 2 | Persistent ^a ≤12 weeks: Continue study therapy. Persistent ^a >12 weeks: Discontinue study therapy |
| | Grade 3 | 1st event: Hold study therapy until resolution to Grade ≤ 1 
 Persistent^a ≤12 weeks: Resume at same dose Persistent^a >12 weeks: Discontinue study therapy 2nd event: discontinue study therapy |
| | Grade 4 | Discontinue study therapy |
| Fatigue | Grade 1 | Continue study therapy |
| | Grade 2 | Persistent ^a ≤12 weeks: Continue study therapy. Persistent ^a >12 weeks: Discontinue study therapy |
| | Grade 3 | 1st event: Hold study therapy until resolution to Grade ≤ 1 
 Persistent^a ≤12 weeks: Resume at same dose Persistent^a >12 weeks: Discontinue study therapy 2nd event: Discontinue study therapy |
| Alopecia | Grade 1 | Continue study therapy |
| | Grade 2 | Persistent ^a ≤12 weeks: Continue study therapy. Persistent ^a >12 weeks: Discontinue study therapy |
| Hemorrhagic events | Grade 1 | Continue study therapy; contact sponsor. |
| | Grade 2 | Persistent ^a ≤12 weeks: Continue study therapy; contact sponsor.. Persistent ^a >12 weeks: Discontinue study therapy |
| | Grade 3 | 1st event: Hold study therapy until resolution to Grade ≤ 1 
 Persistent^a ≤12 weeks: Resume at same dose Persistent^a >12 weeks: Discontinue study therapy 2nd event: discontinue study therapy |
| | Grade 4 or SAE of bleeding any grade | Discontinue study therapy |
| Lab values | Grade 1 | Continue study therapy and monitor in close intervals. |
| | Grade 2 | Persistent ^a ≤12 weeks: Continue study therapy. Persistent ^a >12 weeks: Discontinue study therapy |
| | Grade 3 | 1st event: Hold study therapy until resolution to baseline or Grade ≤1 
 Persistent^a ≤12 weeks: Resume at same dose Persistent^a >12 weeks: Discontinue study therapy 2nd event: Discontinue study therapy |
| | Grade 4 | Discontinue study therapy |
| | | |
| | | |
| Adverse Event | CTCAE Grade | Ibrutinib and Nivolumab * |
| Hematologic Toxicity | | |
| Neutropenia | Grade 1-3 | Continue study therapy; supportive therapy as per local/institutional guidelines |
| | Grade 4 | Supportive therapy as per local/institutional guidelines (hematology assessments twice weekly up to recovery). Any event not recovering to Grade ≤1 within 7 days (±2 days): discontinue study therapy. |

Table 8: Dose Adjustments for Related Non-hematologic and Related Hematologic Toxicities

| | | | | |
|----------------------------|------------------|---|-------------------------------|-------------------------------|
| | | For events recovering to Grade ≤ 1 within 7 days (± 2 days): | | |
| | | Toxicity Occurrence | Starting dose = 560 mg | Starting Dose = 420 mg |
| | | First | Restart at 560 mg | Restart at 420 mg |
| | | Second | Restart at 420 mg | Restart at 280 mg |
| | | Third | Restart at 280 mg | Discontinue study therapy |
| Febrile neutropenia | Grade 3 | Hold study therapy until resolution; supportive therapy as per local/institutional guidelines. Any event not recovering to \leq Grade 1 within 7 days: discontinue study therapy. For events recovering to Grade ≤ 1 within 7 days: | | |
| | | Toxicity Occurrence | Starting dose = 560 mg | Starting Dose = 420 mg |
| | | First | Restart at 560 mg | Restart at 420 mg |
| | | Second | Restart at 420 mg | Restart at 280 mg |
| | | Third | Restart at 280 mg | Discontinue study therapy |
| | | Grade 4 | Discontinue study therapy. | |
| Thrombocytopenia | Grade 1-3 | Continue study therapy; supportive therapy as per local/institutional guidelines | | |
| | Grade 4 | Hold study therapy until baseline or Grade 1; supportive therapy as per local/institutional guidelines: | | |
| | | Toxicity Occurrence | Starting dose = 560 mg | Starting Dose = 420 mg |
| | | First | Restart at 560 mg | Restart at 420 mg |
| | | Second | Restart at 420 mg | Restart at 280 mg |
| | | Third | Restart at 280 mg | Discontinue study therapy |

- a. Persistent treatment-related adverse event that do not recover to Grade ≤ 1 within 12 weeks after last dose of nivolumab.

Table 9: Dose Adjustments for Immune-related Adverse Events

| | | |
|--|--|---|
| Recommendations for the management of immune-related adverse events and adverse events of clinical interest are provided in Section 8. | | |
| Adverse Event | CTCAE Grade | Ibrutinib and Nivolumab |
| Immune-related AE (irAE) | Section 8: Guidelines for Management of Immune Related Adverse Events | |
| | Grade 1 | Continue study therapy. |
| | Grade 2 | Consider hold study therapy until resolution to Grade ≤ 1 Persistent ^a ≤ 12 weeks: Continue therapy at same dose and schedule. Persistent ^a > 12 weeks: Discontinue study therapy |
| | Grade 3 | 1st event: hold study therapy, resume only after discussion/agreement with sponsor and resolution to Grade ≤ 1 2nd event: discontinue study therapy |
| | Grade 4 | Discontinue study therapy. |
| Recommendations for the management of immune-related adverse events and adverse events of clinical interest are provided in Section 8. | | |
| Adverse Event | CTCAE Grade | Ibrutinib and Nivolumab |
| Infusion Reaction | Section 8.11 (Table 18): Management of Nivolumab Related Infusion Reactions | |
| | Grade 1 | Continue study therapy. |
| | Grade 2 | Hold study therapy until resolution to Grade ≤ 1 1st event: resume at same dose and schedule. 2nd event (despite pre-medication, antihistamines, non-steroidal anti-inflammatory drugs, corticosteroids, bronchodilators, IV fluids; |

Table 8: Dose Adjustments for Related Non-hematologic and Related Hematologic Toxicities

| | | |
|--|---|---|
| | | prophylactic medications indicated for <24 hours]); discontinue study therapy. |
| | Grade 3 and 4 | Discontinue study therapy. |
| Enterocolitis or diarrhea | Section 8.1. (Table 10): Management of Gastrointestinal Adverse Events | |
| | Grade 1 | Continue study therapy. |
| | Grade 2 | 
1st event: Hold until resolution to Grade ≤ 1.
 
 Improvement to \leq Grade 1: Resume study therapy at same dose and schedule. Worsening or persistence >3 days from day of onset despite oral steroid treatment: discontinue study therapy. 
2nd event: discontinue study therapy
 |
| | Grade 3 and 4 | Discontinue study therapy. |
| Renal/Creatinine | Section 8.5. (Table 14): Management of Renal Adverse Events | |
| | Grade 1 | Continue study therapy. |
| | Grade 2 and 3 | 
1st event: Hold until resolution to Grade ≤ 1.
 
 Improvement to \leq Grade 1: Resume study therapy at same dose and schedule. Worsening or persistence >7 days from day of onset: Discontinue study therapy. 
2nd event: discontinue study therapy
 |
| | Grade 4 | Discontinue study therapy. |
| Pneumonitis | Section 8.7. (Table 16): Management of Pulmonary Adverse Events | |
| | Grade 1 | 
Consider holding study therapy.
 
Improvement to baseline: resume dosing.
 
Worsening or persistence >7 days from day of onset: hold study therapy and treat as Grade 2.
 |
| | Grade 2 | 
Hold study therapy until resolution to Grade ≤ 1
 
Improvement to Grade ≤ 1 within 2 weeks: resume dosing.
 
Persistence for >2 weeks from day of onset: Discontinue study therapy.
 |
| | Grade 3 and 4 | Discontinue study therapy. |
| Hepatic alteration | Section 8.2. (Table 11): Management of Hepatic Adverse Events | |
| | Grade 1 | 
Continue study therapy.
 
Worsening or persistence >7 days from day of onset: hold study therapy and treat as Grade 2.
 |
| | Grade 2 | 
Hold study therapy until resolution to Grade ≤ 1.
 
Improvement to Grade ≤ 1 within 2 weeks: resume at same dose and schedule.
 
Persistence for >2 weeks from day of onset: Discontinue study therapy.
 |
| | Grade 3 and 4 | Discontinue study therapy. |
| AST/ALT and Bilirubin | Section 8.2. (Table 11): Management of Hepatic Adverse Events | |
| | Grade 1 | Continue study therapy. If worsens treat as Grade 3. |
| | Grade 2 | 
Consider hold study treatment until resolution to Grade ≤ 1
 
Persistent^a ≤ 12 weeks: Continue therapy at same dose and schedule.
 
Persistent^a >12 weeks: Discontinue study therapy
 |
| | Grade 3 and 4 | Discontinue study therapy |
| Recommendations for the management of immune-related adverse events and adverse events of clinical interest are provided in Section 8. | | |
| Adverse Event | CTCAE Grade | Ibrutinib and Nivolumab |
| Endocrinopathy | Section 8.3. (Table 12): Management of Endocrinopathies | |
| | Asymptomatic | Continue study therapy. |
| | Symptomatic | Abnormal lab values and pituitary MRI scan: Hold study therapy until improvement to Grade ≤ 1 ; resume at same dose and schedule. |

Table 8: Dose Adjustments for Related Non-hematologic and Related Hematologic Toxicities

| | | |
|-------------------------------------|---|---|
| | Suspicion of adrenal crisis | Hold study therapy; discontinue study therapy if no improvement after adrenal hormone replacement. |
| Rash | Section 8.4. (Table 13): Management of Rash | |
| | Grade 1 | Continue study therapy. |
| | Grade 2 | Persistent ^a ≤12 weeks: Continue therapy at same dose and schedule. Persistent ^a >12 weeks: Discontinue study therapy |
| | Grade 3 | Hold study therapy until resolution to ≤ Grade 1 Persistent >2 weeks or inability to reduce steroid ≤10 mg/day >12 weeks: Discontinue study therapy. Discontinue if Grade 3 rash recurs. |
| | Grade 4 | Discontinue study therapy |
| Neurological | Section 8.6. (Table 15): Management of Neurological Adverse Events | |
| | Grade 1 | Continue study therapy. |
| | Grade 2 | Hold study therapy until improvement to Grade ≤1; then resume study therapy. |
| | Grade 3 and 4 | Discontinue study therapy. |
| Uveitis or visual complaints | Section 8.8. (Table 17): Management of Uveitis and Visual Complaints | |
| | Grade 1 | Consider hold study therapy. |
| | Grade 2 | Hold study therapy until improvement to Grade ≤1; then resume study therapy. Persistence for >2 weeks from day of onset despite symptomatic treatment: Discontinue study therapy. |
| | Grade 3 and 4 | Discontinue study therapy. |

- a. Persistent treatment-related adverse event that do not recover to Grade ≤1 within 12 weeks after last dose of nivolumab.

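### Footnote a of Tables 8 and 9 counts 12-week persistence from the last nivolumab dose, so read literally the Grade 2 persistence rule in six rows is inoperative while nivolumab continues

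*Protocol*

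**What the plan says.** **The Grade 2 cells (Protocol 6.4.3).** In Table 8, the Grade 2 cells for General, Fatigue, Alopecia, Hemorrhagic events and Lab values have two branches. Below the threshold, the cell reads (after its ≤ sign) "12 weeks: Continue study therapy"; the hemorrhagic cell adds that the sponsor is to be contacted. Above it, the cell reads "Persistent ^a >12 weeks: Discontinue study therapy". The Table 9 Rash Grade 2 cell has the same two branches. The Table 9 Grade 2 cells for general immune-related events and for AST/ALT and bilirubin use the same 12-week threshold but let the investigator consider a hold.

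**The footnote.** Under both tables, superscript a is explained as "Persistent treatment-related adverse event that do not recover to Grade ≤1 within 12 weeks after last dose of nivolumab". The operative words are "within 12 weeks after last dose of nivolumab".

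**The dosing schedule.** Protocol 6.1.2: "Nivolumab will be administered on Day 1 of each 14-day treatment cycle". Protocol 6.3: "Subjects may receive nivolumab infusions with no less than 12 days between doses and no more than 3 days after the scheduled dosing date", and "A maximum delay of 42 days between doses is allowed".

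**The limit on delay.** Protocol 6.4.3: "If treatment is delayed > 6 weeks, the subject must be permanently discontinued from study therapy, except as specified in the protocol". Section 11.2 lists an interruption of more than 6 weeks as a ground for stopping, unless the sponsor approves it for reasons not related to drug.

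**Other Grade 2 rows in Table 9.** Enterocolitis or diarrhea, renal, pneumonitis, hepatic alteration and uveitis each state a persistence limit (3 days, 7 days or 2 weeks) counted from day of onset. None of them uses footnote a.

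**The concern.** A persistence rule needs a start date that stays fixed while the event lasts. Footnote a ties the start to the last nivolumab dose, and the cells that use it tell the site to keep giving nivolumab. Read literally, the first branch of the cell prevents the second from being reached.

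The table itself gives a careful site no way to settle this. Where its authors wanted a count from onset, they wrote that. Footnote a says something different, so a site that counts from onset in the footnoted rows departs from the text, and a site that follows the text does not reach the stopping branch while nivolumab continues. Both could believe that they comply.

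What is at stake is how a long-lasting related Grade 2 event is handled, including a hemorrhagic one. Some reported outputs would also depend on the reading: SAP 5.1 summarises adverse events leading to treatment discontinuation and by action taken, and SAP 3.4 summarises exposure.

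**Working it through.** The plan states no figure to reproduce. The check compares the longest time since the last nivolumab dose with the time that the rule requires.

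**Inputs**
- Threshold: 12 weeks × 7 = 84 days (footnote a).
- Dosing interval: 14 days (6.1.2).
- Late window: 3 days (6.3).
- Maximum delay between doses: 42 days (6.3); the discontinuation limit is 6 weeks × 7 = 42 days (6.4.3 and 11.2).
- DLT window: 28 days (3.3.1).

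**Reading 1: last dose means the most recent dose, and nivolumab continues.** Time since last dose cannot exceed the gap between doses.

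| Dosing pattern | Longest time since last dose | Needed |
|---|---|---|
| On schedule | 14 days | more than 84 |
| With window | 14 + 3 = 17 days | more than 84 |
| Maximum permitted gap | 42 days | more than 84 |

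If the 42-day delay is instead read as added to the 14-day interval, the gap is 14 + 42 = 56 days, still short of 84. On schedule, 84 days spans 84 / 14 = 6 dosing intervals, so the count restarts at each of them. A day-by-day check over 2 years, with onset assumed on day 20 after the first nivolumab dose (day 0), found no day on which the rule fired at gaps of 14, 17 or 42 days.

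**Reading 2: last dose means the last dose before onset.** The reference date is now fixed, and the rule fires 85 days after it. For the same assumed onset on day 20:
- 14-day gaps: last dose day 14, so 14 + 85 = day 99.
- 17-day gaps: last dose day 17, so 17 + 85 = day 102.
- 42-day gaps: last dose day 0, so 0 + 85 = day 85.

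An unresolved Grade 2 event on schedule therefore leads to discontinuation at day 99 under one reading, and to no discontinuation by this rule under the other.

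**Nivolumab stopped, ibrutinib alone (6.4).** If nivolumab was last given on day 28 and onset is on day 30 (both assumed), the rule fires at 28 + 85 = day 113.

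**Therapy held.** The count from last dose then runs, but the 42-day limit is reached at half of 84 days. The Table 8 Grade 3 cells for General, Fatigue, Hemorrhagic events and Lab values show the conflict: they hold therapy and allow it to resume at the same dose when persistence is 12 weeks or less, while 6.4.3 requires permanent discontinuation after a delay of more than 6 weeks. Section 6.4.3 allows exceptions specified in the protocol, but no text says that footnote a is one. The exception in 11.2 is for non-drug-related reasons, whereas Table 8 covers related toxicity.

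**Dose-limiting toxicity.** An event that requires discontinuation under Tables 8 and 9 can count as a DLT, but 84 days exceeds the 28-day window. Within Part A's DLT window the rule cannot fire whether the last dose is the most recent one or the last before onset.

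**The case against.** A reader might infer that the 12-week rule can never fire. The documents do not support that. Section 6.4 allows ibrutinib alone after consultation with the sponsor, and the count then runs, although Amendment 7 ends this except for subjects rolling over to the extension study. The count also runs during a hold, subject to the 6-week limit. And the footnote does not say most recent: read as the last dose before onset, the rule works.

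A reader might also infer that this is the only discontinuation rule for persistent Grade 2 toxicity, or that Table 9 generally says to continue at Grade 2. Neither is so. Five Table 9 rows have their own Grade 2 persistence limits from day of onset, and most other Table 9 Grade 2 rows hold therapy. Section 9.2 makes failure to reduce corticosteroids within 12 weeks a reason to stop, and section 11.2 lets the investigator stop for safety or unacceptable toxicity. In the hemorrhagic rows the sponsor is contacted at Grade 2, and a serious bleed of any grade leads to discontinuation, so a long Grade 2 bleed would not go unseen.

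Finally, differing practice between sites is a possibility, not something that the documents show. The Amendment 7 rationale says that the primary and secondary objectives have been analysed and published, so a correction now reaches only subjects still on treatment.

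These points limit the scope and the consequence. They leave the core untouched: the six rows prescribe neither a hold nor ibrutinib alone, and a rule that works only under a reading the footnote does not state still needs to be clarified.

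**Conclusion.** The point holds as an internal inconsistency in the wording. In six Grade 2 rows the persistence rule, read literally, is inoperative while nivolumab continues: at most 14, 17 or 42 days since the last dose, against 84. Two further rows (Table 9 general immune-related events, and AST/ALT and bilirubin) share the defect when the investigator does not hold. The anchor also differs from that of other rows in Table 9, and in held rows the 12-week count conflicts with the 42-day and 6-week limits.

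This rests on two assumptions: that the last dose means the most recent one, and that nivolumab continues at permitted gaps. General grounds for stopping remain available throughout. DLT counts are unaffected. The effect on exposure and on discontinuations cannot be sized, because the documents do not say how many subjects had long-lasting Grade 2 events or how sites read the footnote.

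**What to change.** Reconcile footnote a of Tables 8 and 9 with the Grade 2 cells that use it, and with the 42-day maximum in section 6.3 and the 6-week limits in sections 6.4.3 and 11.2. State one unambiguous reference date for the 12-week count, and say whether the 12-week rows fall under the exception in 6.4.3. The choice of date, and which limit prevails, belongs to the sponsor's medical team.

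The cost is a short amendment, mainly two footnotes. Once the rule is operable, some subjects with long-lasting Grade 2 events may be handled differently from before.
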